The investigators should document all prior significant medical history. Additional conditions present at the time when informed consent is given and up to the time of first infusion (Week 0) are to be regarded as concomitant conditions.

Illnesses first occurring or detected during the study and/or worsening of a concomitant condition during the study should be documented as AEs in the CRF.

Prior and concomitant medications

All medications, including over-the-counter treatments and preventative vaccines taken by the patient during the study, including those treatments initiated prior to the start of the study, must be recorded in the CRF. The entry must include the dose, regimen, route, indication, and dates of use.

Study Procedures

Table 2 outlines the timing of procedures, and assessments to be performed throughout the study.

Table 2. Schedule of Assessments

Visit Number	1	2	3	4	5	6	7	8	9
Weeks	N/A	Week 0	Week 2	Week 6	Week 10	Week 14	Week 18	Week 22	Week 26
Visit Name	Screening (Phone call)	Infusion- 1 /Baseline	Infusion 2	Infusion 3	Infusion 4	Infusion 5	Follow Up	Follow Up	EOS
Window Period	Up to 14 days	± 3 days	± 3 days	± 3 days	± 3 days	± 3 days	± 3 days	± 3 days	± 3 days

STUDY PROCEDURES

Informed Consent	X	X							
Inclusion and Exclusion Criteria	X	X							
Pre-infusion assessment		X	X	X	X	X			
Review of Medical History	X	X	X	X	X	X	X	X	X
Concomitant Medication Review	X	X	X	X	X	X	X	X	X
Vital Signs		X	X	X	X	X	X	X	X
Weight and Height ¹		X	X	X	X	X	X	X	X
Physical Examination		X	X	X	X	X	X	X	X
SF-36 Questionnaire		X	X	X	X	X	X	X	X
PHQ-9		X	X	X	X	X	X	X	X
Rapid antibody COVID-19		X							X
CBC with differential		X		X		X			X
Chemistry		X		X		X			X
Coagulation Panel		X		X		X			X
CRP		X		X		X			X
IL-6		X		X		X			X
IL-10		X		X		X			X
TNF α		X		X		X			X
HB-adMSCs Administration		X	X	X	X	X			
24-hour telephone encounter		X	X	X	X	X			
Adverse Event Monitoring		X	X	X	X	X	X	X	X

¹ Height will only be measured at baseline

Informed Consent (ICF)

Prior to commencement of any trial related activity, the investigator or designated staff will obtain written informed consent from the patient.

Patient Re-Screening

If a patient is screened and fails to meet any study entry criteria may be re-screened only once. Such patient must be fully consented a second time before the second set of screening assessments take place and shall be assigned a new subject number. Investigator discretion should be exercised in determining who may be re-screened.

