If a patient is enrolled after they have been re-screened, such subject shall be assigned a new subject ID number, different from the previous attempt to enroll.

Assessments by Week

Assessments will occur as outlined in the following subsections. For visits at Weeks 0 through 26, there will be a window of ± 3 days.

Screening

The Screening visit will last up to 14 days. These are the procedures to be performed during this visit:

- Demographic Information will be obtained.
- Medical History and Current conditions will be obtained,
- Concomitant Medications will be obtained. Every medication listed should match a condition in the medical history.
- Ascertain patient eligibility by evaluating patient results against the inclusion/exclusion criteria.

Upon completion of all Screening procedures, the Principal Investigator must confirm and document the patient eligibility in the “Screening Result” CRF and notify the Sponsor via Fax or e-mail.

Infusion Visits (Baseline/Week 0, Week 2, Week 6, Week 10, and Week 14)

Generally, these are the procedures to be performed at every infusion visit. For details please refer to the schedule of assessments.

Baseline assessments will be taken before the administration of the first infusion. A second assessment of informed consent shall be obtained prior to the first infusion.

- Pre-infusion assessment will be made by telephone call in the morning prior to all infusion visits to assess any occurrence of symptoms. In the event a subject is exhibiting symptoms, the subject will be asked to remain home.
- Weight and height will be measured
- Vital Signs will be measured.
- Concomitant medications will be reviewed and updated if necessary.
- Medical History will be reviewed and updated if necessary. If the patient reported a medication which does not match the current medical history, further investigation will be required to determine whether it was added due to an Adverse Event, or the patient just forgot to mention it before. If it is found to be an AE, it should be recorded in the appropriate CRF. If the patient forgot to mention it before, a note to file (NTF) should be made to clarify the case.
- Blood will be collected for laboratory assessments at weeks 0, 6, and 14.
- Physical examination performed by principal investigator or sub-investigator.
- Administer investigational product.

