Vital signs (body temperature, pulse, oxygen saturation, systolic and diastolic blood pressure measurements) will be evaluated at the visits indicated in the schedule of assessments. It is important that all vital signs be measured after the patient has been resting in a sitting position for at least 5 minutes. Blood pressure measurements are to be taken in the same arm for the duration of the study. Body weight (without coats and shoes) will be recorded whenever vital signs are recorded, and height (without shoes) will be recorded at Infusion 1 (baseline) only.

Vital sign measurements will be repeated if clinically significant or machine/equipment errors occur. Out-of-range blood pressure and pulse measurements will be repeated at the Investigator's discretion. Any confirmed, clinically significant vital sign measurements will be recorded as AEs and followed up as such.

Physical Examination

A complete physical examination (head, eyes, ears, nose, throat, heart, lungs, abdomen, skin, cervical and axillary lymph nodes, neurological, and musculoskeletal systems) will be performed at Infusion 1 (Baseline).

A limited physical examination to verify continued patient eligibility and to follow up any change in medical history will be performed at the visits indicated in the schedule of assessments. Symptom-driven physical examinations will be performed as clinically indicated at any study visit. All changes not present at baseline or described in the past medical history and identified as clinically noteworthy will be recorded as AEs.

Clinical Laboratory Parameters

The Investigator must review all laboratory reports and document the review. Any laboratory test result or change considered by the Investigator to be clinically significant should be considered an AE and recorded in the AE CRF. Clinically significant abnormal values occurring during the study will be followed until repeat test results return to normal, stabilize, or are no longer clinically significant.

Laboratory tests to be performed during the study:

Complete Blood Count with Differential	Il-10
Chemistry	IL-6
Coagulation study (PTT/PT/INR)	Tumor Necrosis Factor alpha
C Reactive Protein	Rapid Antibody Test COVID-19

Adverse Events

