5.3.2.1. Adverse Events

AEs will be coded using the most recent version of the Medical Dictionary for Regulatory Activities (MedDRA).

A treatment emergent adverse event (TEAE) is defined as an event that has onset date on or after the first day of exposure to infusion treatment and on or before the last day of infusion treatment. Here the first day of exposure is defined as the first day of exposure to infusion treatment.

Treatment Adverse events (TAES) are summarised descriptively, whereas non-TEAEs are presented in listings. TAE data will be displayed in terms of the number of subjects with at least one event (N), percentage of subjects with at least one event (%) and the number of events (E).

Individual adverse events will be listed.

The details of the planned displays are in programming specification document.

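### Laboratory and vital-sign findings made before the first infusion can be counted as treatment emergent under SAP 5.3.2.1, while SAP 7.1.5 and other protocol sections point the other way

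*Protocol*

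**What the plan says.** **Timing.** In Table 2 of the protocol, screening is a telephone contact with no blood test, vital signs or examination. These first appear at Visit 2, which is both baseline and the first infusion visit. Under Infusion Visits: "Baseline assessments will be taken before the administration of the first infusion" and "Blood will be collected for laboratory assessments at weeks 0, 6, and 14". SAP 7.1.6 makes the day of first dose Study Day 1.

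**What becomes an AE.** Three neighbouring protocol sections give three rules:
- Clinical Laboratory Parameters: "Any laboratory test result or change considered by the Investigator to be clinically significant should be considered an AE".
- Vital Signs, Height, and Weight: "Any confirmed, clinically significant vital sign measurements will be recorded as AEs".
- Physical Examination: "All changes not present at baseline or described in the past medical history and identified as clinically noteworthy will be recorded as AEs".

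Only the third exempts what was already there at baseline. Two further sections bear on the same findings. Prior and concomitant conditions says that conditions present at consent and "up to the time of first infusion (Week 0) are to be regarded as concomitant conditions". The general definition under Adverse Events makes something present at screening an AE only if it worsens.

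**What becomes a TEAE.** SAP 5.3.2.1 takes an "event that has onset date on or after the first day of exposure to infusion treatment", up to the last day of infusion treatment. It mentions neither time of day nor worsening. The table in SAP 7.1.5 flags events before the first dose as Y for treatment emergent, and events on or after it as N.

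**The concern.** A Week 0 value is pre-treatment by design, and SAP 5.1.2 uses it as the baseline for that reason. Yet if that value is judged clinically significant, entered as an AE and given a Day 1 onset, SAP 5.3.2.1 classes the event as treatment emergent. The same measurement is then both the pre-treatment reference and an on-treatment event.

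This matters here because eligibility admits people with diabetes, cancer, heart disease and autoimmune disease, in whom clinically significant baseline values are plausible. There is no control arm against which to compare the TEAE rate. Day 1 also carries the vital signs taken during and after the infusion, so a rule based on date alone mixes pre-infusion readings with those meant to detect an acute reaction. Finally, whether a Week 0 abnormality enters the AE data at all depends on which protocol section the site follows.

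**Working it through.** The plan states no figure to reproduce. The check is to apply the rules to dated events, then to size the result under stated assumptions.

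**Step 1: the date rules applied.** Day 1 is the first dose; the last infusion at Week 14 is Day 14 × 7 + 1 = 99.

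| Event | SAP 5.3.2.1 | SAP 7.1.5 as written | SAP 7.1.5 with Y and N exchanged |
|---|---|---|---|
| Onset dated Day −7 | not a TEAE | Y | N |
| Pre-infusion finding, onset dated Day 1 | TEAE | N | Y |
| Post-infusion event, Day 1 | TEAE | N | Y |
| Week 6 finding, Day 43 | TEAE | N | Y |

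The second and third rows are identical in every column: no version separates a pre-infusion from a post-infusion Day 1 event. SAP 7.1.5 as written keeps the pre-infusion finding out only by also excluding every genuine post-infusion event.

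**Step 2: do other protocol sections keep the finding out of the AE data?** Not reliably.
- The concomitant-conditions section would, but its next paragraph makes illnesses that first come to light during the study AEs. An abnormality found at Week 0 fits both descriptions.
- The worsening rule under Adverse Events is tied to screening, a telephone call at which nothing is measured. The same section then repeats that significant laboratory abnormalities are AEs, again with no exemption.
- Inclusion criterion 5 concerns signs of infection and names temperature and pulse. It does not limit blood pressure or laboratory values.

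**Step 3: number of subjects.** Let p be the share of the 55 subjects with a pre-infusion finding recorded as an AE with Day 1 onset. The documents give no value, so p is an assumption. Expected number = 55p; chance of at least one = 1 − (1 − p)^55, treating subjects as independent.

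| p | Expected subjects | Chance of at least one |
|---|---|---|
| 2% | 1.1 | 67% |
| 5% | 2.75 | 94% |
| 10% | 5.5 | 99.7% |
| 20% | 11 | above 99.9% |
| 30% | 16.5 | above 99.9% |

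**Step 4: effect on incidence.** Let t be the TEAE incidence without these findings (also assumed).
- Independence: reported incidence = 1 − (1 − t)(1 − p).
- Full overlap (the smaller group lies within the larger): reported incidence = max(t, p).

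For t = 40%:
- independence gives 1 − 0.60 × 0.90 = 46% at p = 10%, and 1 − 0.60 × 0.70 = 58% at p = 30%;
- full overlap gives 40% at both.

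For t = 20%:
- independence gives 1 − 0.80 × 0.90 = 28% and 1 − 0.80 × 0.70 = 44%;
- full overlap gives 20% and 30%.

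**The case against.** A reader might infer that every pre-existing abnormality will be counted as a TEAE. The documents do not support that:
- SAP 7.1.5 as written gives N for the same event.
- The concomitant-conditions section and the general AE definition give a site grounds to record the finding as history.
- The rules turn on onset, and nothing makes the sampling date the onset date. A chronic condition may properly be dated before Day 1, which SAP 5.3.2.1 excludes.
- Only results judged clinically significant (and confirmed, for vital signs) are in scope.

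All of this stands, and it makes the point conditional. It does not remove it, because these texts conflict with the laboratory and vital-sign rules and nothing ranks them.

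A reader might also infer that, without a control arm, such events can never be separated out. That goes too far. Each AE is assessed for relationship to study drug and listed individually, and the stated endpoint is drug-related AEs and SAEs. A finding from a pre-infusion sample is unlikely to be judged related, so that endpoint is largely protected.

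Nor do the documents show that the reported TEAE rate will be too high on balance. The same SAP definition closes the window on the last infusion day, which leaves out events arising after that day, through Week 26. That works in the opposite direction.

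Finally, the study is descriptive with no hypothesis test, and subjects with abnormal baselines may well be those with later events, so the independence figures may overstate the effect. Both points are fair and limit the weight of the concern.

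**Conclusion.** The point holds in conditional form. A clinically significant laboratory or confirmed vital-sign finding made before infusion 1, if recorded as an AE with Day 1 onset, is a TEAE under SAP 5.3.2.1 although it preceded treatment. The protocol does not settle whether it should be recorded as an AE, and SAP 7.1.5 either reverses the definition or, with its entries exchanged, shares the gap.

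The exposure is in the all-cause TEAE count. It is about 1 to 17 of 55 subjects if 2% to 30% have such a finding so recorded. For a true incidence of 40% and 10% to 30% affected, the reported figure would run from 40% with full overlap to 46% to 58% under independence. Prevalence, true incidence and degree of overlap are all assumptions. The primary efficacy summaries are untouched. It is worth correcting because the remedy is a matter of wording and the TEAE tables are a main safety output of a single-arm study.

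**What to change.** 1. **Protocol.** Reconcile Prior and concomitant conditions, the laboratory and vital-sign rules, and the general AE definition. Give the laboratory and vital-sign sentences the baseline exemption already used for the physical examination. Findings from the Week 0 pre-infusion assessment are then recorded as concomitant conditions and become AEs only on worsening.
2. **SAP 5.3.2.1.** Define a TEAE by onset or worsening after the start of the first infusion. For Day 1 events use the infusion start time, which the protocol already requires to be recorded. State that findings from the pre-infusion Week 0 assessment are not TEAEs. This covers a result that reaches the site later and is dated by the report rather than the sample.
3. **SAP 7.1.5.** Correct the Y and N entries and the date condition so that the table matches the revised 5.3.2.1.

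The cost is a few sentences and an onset-time (or before/after infusion) field for Day 1 events. No visit or test is added.

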For the purposes of this study, the period of observation for collection of AEs extends from the time the patient gives informed consent through Week 26 (or early discontinuation visit). Follow-up of the AE is required until the event resolves or stabilizes at a level acceptable to the Investigator.

Intensity of Adverse Event

The intensity of the AE will be judged based on the following:

Mild	Awareness of sign(s) or symptom(s) which is/are easily tolerated
Moderate	Enough discomfort to cause interference with usual activity
Severe	Incapacitating or causing inability to work or to perform usual activities

Infusion Stopping Rules

Infusion will be stopped when:

- Allergic reaction is aroused after the product has been administered intravenously.
- Patient verbally decline the treatment at any moment prior, or during the infusion.

- Hyperpyrexia develops after infusion administration begins (core body temperature greater than or equal to 40°C) [57].
- PI may stop the study at any time, based upon PI's discretion
- Malignant Hypertension (180/120 mm/Hg)
- Sudden Severe Hypotension (30-40 mm/Hg drop from pre-infusion level)

Study Alteration Rules

If any of the following events listed below occur, administration of the study drug will be immediately suspended. The Internal Monitoring Committee (IMC), presided by the Medical Monitor will meet to review the incident and its etiology. The committee determine if it is likely related to the drug, the infusion or unrelated. If the IMC along with the Medical Monitor agree that the SAE is unlikely or unrelated to the drug, the study will be continued. If the SAE appears to be definitely drug-related, the study will be stopped. If the SAE is probably or possibly linked to the drug, the IMC will determine the risk to future patients and decide if the study should proceed or be stopped.

Study Stopping Rules

The stopping rules listed below will trigger cessation of enrollment and potential study closure pending a comprehensive DSMB safety review.

1. Any infusion related death, deemed by PI to be associated or possibly associated with study drug.
2. Three or more of the same Grade 3 or higher AEs (judged by the investigator, medical monitor or sponsor), including infusion site reactions.
3. Any event which, in the opinion of the investigator, medical monitor or sponsor, contraindicates further dosing of additional subjects.

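### The Study Alteration Rules suspend dosing without listing the triggering events, and if the five stopping events are meant, the IMC's decision to continue is not put in order with the DSMB review

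*Protocol*

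**What the plan says.** Two consecutive protocol sections deal with halting the study for safety.

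**Study Alteration Rules.** The opening sentence reads "If any of the following events listed below occur, administration of the study drug will be immediately suspended". One paragraph on review by the IMC follows, with the Medical Monitor presiding. It gives three outcomes:

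- SAE unrelated, or unlikely to be related: "If the IMC along with the Medical Monitor agree that the SAE is unlikely or unrelated to the drug, the study will be continued".
- SAE definitely drug-related: the study stops.
- SAE probably or possibly linked: "the IMC will determine the risk to future patients and decide if the study should proceed or be stopped".

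The section ends there, without a list of events.

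**Study Stopping Rules.** This section has its own heading and lead-in: "The stopping rules listed below will trigger cessation of enrollment and potential study closure pending a comprehensive DSMB safety review". Five numbered events follow. Rule 2 is "Three or more of the same Grade 3 or higher AEs (judged by the investigator, medical monitor or sponsor), including infusion site reactions". After the list, the protocol says that restarting dosing may be considered once that review has taken place.

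**The concern.** The Alteration Rules contain the protocol's only express study-wide suspension of dosing, and its trigger has to be inferred. The Stopping Rules expressly halt enrollment only. Once enrollment is complete that halt protects nobody, while enrolled patients may still have infusions due up to Week 14.

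If the five stopping events are the triggers, one event starts two processes under two bodies, and neither section refers to the other's body. Staff who follow the Alteration Rules literally could resume infusions on the IMC's decision before the DSMB has reviewed the event. What is at stake is patient safety and uniform conduct, not a statistical result.

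**Working it through.** No arithmetic applies, and the plan gives no figure to reproduce. The check is a side-by-side reading of the two sections, plus a search of both documents for the IMC, the DSMB and the Medical Monitor.

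| Question | Study Alteration Rules | Study Stopping Rules |
|---|---|---|
| Trigger | Points to a list below; 0 events under the heading | 5 numbered events |
| Halted expressly | Dosing | Enrollment |
| Halted by implication | – | Dosing, through the later sentence on resuming it |
| Reviewing body | IMC, with the Medical Monitor presiding | DSMB |
| What ends the hold | Unlikely or unrelated: study continues. Probably or possibly linked: IMC decides | DSMB review, after which resuming dosing may be considered |
| Other body named? | DSMB: no | IMC: no |

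**Step 1: the trigger.** The Infusion Stopping Rules and the SAE definition both stand above the Alteration Rules, so neither can be the list below. The only study-level list further down is the five stopping events. They are the natural candidate, although they have a separate heading, a separate lead-in and a different stated consequence.

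**Step 2: the outcomes.** Of the three IMC outcomes, two allow the study to continue (unlikely or unrelated; probably or possibly linked). The third, a mandatory stop, conflicts with nothing.

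**Step 3: one event through both sections.** Suppose three patients have the same Grade 3 or higher adverse event, each is hospitalized, and the IMC judges the events unrelated to the drug.

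- Rule 2 is met, because it asks for no link to the drug.
- Each event is an SAE, because hospitalization is one of the protocol's criteria for seriousness.
- Under the Alteration Rules, the study continues once the IMC and the Medical Monitor agree.
- Under the Stopping Rules, enrollment is held for the DSMB, and resuming dosing is considered only after its review.

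The case is foreseeable. Hospitalization for COVID-19 is a primary endpoint in a high-risk population, and the protocol's AE definition applies whatever the suspected cause. Three such hospitalizations would meet rule 2 on the assumption that each is graded 3 or higher.

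**Step 4: the other stopping rules.** The overlap is less clear for these. Rule 1 is "Any infusion related death, deemed by PI to be associated or possibly associated with study drug", so it already carries a finding of at least possible association and meets the Alteration Rules mainly through the probable-or-possible outcome. Rule 3 rests on an opinion that the event "contraindicates further dosing of additional subjects", and an IMC restart against that opinion is implausible. Rules 4 and 5 start from a link to the infusion, and rule 5 already involves the safety monitor or the DSMB. The point therefore rests on rule 2.

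**Step 5: wording of the outcomes.** All three outcomes speak of an SAE. Rule 2 counts adverse events by grade, and the protocol classifies seriousness separately. A rule 2 event that is not serious therefore has no outcome under the Alteration Rules.

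**Step 6: precedence.** No sentence in the protocol or the SAP says which body acts first or whose decision prevails. The SAP does not deal with the matter.

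**The case against.** The strongest reply is that the two sections can both be obeyed. The five events do stand below the Alteration Rules, so the defect may be no more than a loose cross-reference. The sentence on resuming dosing already implies that the DSMB review comes first. Continuing the study need not mean that infusions restart or that the DSMB hold lifts. Much of this stands: the cumulative reading is possible and sensible. But no text states it, and a rule for suspending dosing should not depend on staff working it out.

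Existing safeguards also count. The synopsis has the Medical Monitor overseeing the whole study, and both the Medical Monitor and the DSMB monitoring patient safety data. The PI may stop the study at any time, the sponsor or a regulator may terminate it, and an infusion may be held for a patient's ongoing AE. These lower the risk, but they supply neither the trigger nor the order of decisions.

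A reader might infer more than the documents support:

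- *That the suspension can have no trigger at all.* The stopping events are a reasonable candidate. A list could also have been lost when the text was read from PDF, although no figure or redaction marker appears there.
- *That the IMC is empowered to override the DSMB.* The protocol gives no precedence either way.
- *That a non-serious rule 2 event escapes review.* It still halts enrollment and goes to the DSMB.
- *That an SAE put down to the infusion has no outcome, because "The committee determine if it is likely related to the drug, the infusion or unrelated" names the infusion separately.* Such an event, if not attributed to the drug, falls literally under the unrelated-to-the-drug outcome.

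**Conclusion.** The point holds in a limited form, and the text is wrong as written. The trigger for the only express dosing suspension must be inferred. On the natural inference, a serious rule 2 event judged unrelated is told to continue by one section and to wait for the DSMB by the other.

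In size, this is one clear conflict case, arising from the outcome that continues the study. Its frequency cannot be estimated, because the documents give no event rates. Sample size, power and error rates are untouched.

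The conclusion rests on two assumptions: that no list was lost from the Alteration Rules section, and that the stopping events are the intended triggers. If a different list was intended, the conflict may not arise in this form, but the missing list would still need to be supplied. The change should be made because the rule protects participants and cannot be applied uniformly as it stands.

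**What to change.** Amend the protocol as follows:

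1. In the Study Alteration Rules, cross-refer to stopping events 1–5, or insert the list that was intended.
2. State that any stopping event suspends both dosing and enrollment.
3. State that an IMC decision to continue does not lift the hold, and that neither dosing nor enrollment resumes until the DSMB review is complete.
4. Keep the mandatory stop for a definitely drug-related SAE. In the other two outcomes, refer to the event and not to the SAE, so that a non-serious rule 2 event is covered.

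This needs no extra data or patients. The cost is possible delay: a restart may have to wait for the DSMB, and an infusion due meanwhile may miss its ± 3 day window (protocol, Assessments by Week). A subject who misses an infusion altogether would leave the efficacy analysis set, which requires all 5 infusions (SAP section 4) and is used for the primary analysis (SAP section 5.2). A prompt DSMB review would limit that loss.
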